## PROTOCOL SYNOPSIS

Title	A Safety Study of Intravenous Infusion of Bone Marrow Mesenchymal Stem Cell-derived Extracellular Vesicles (UNEX-42) in Preterm Neonates at High Risk for Bronchopulmonary Dysplasia
Study Phase	Phase 1
Indication	Bronchopulmonary dysplasia (BPD) prevention in preterm infants
Primary Objective	To assess the safety and tolerability of intravenous (IV) infusion of UNEX-42 in infants born at <27 weeks of gestational age (GA) and exhibiting respiratory distress.
Secondary Objective(s)	
To assess the effect of UNEX-42 on the following:
 
 
Incidence and severity (mild, moderate, severe) of BPD or death at 36 weeks postmenstrual age (PMA)
 
Short-term outcomes including oxygen and ventilation exposure in the first 28 days after treatment.
 
Long-term outcomes up to 1 year (corrected age).
 

Study Design	A multicenter, placebo-controlled, randomized, dose escalation, safety, and tolerability study of UNEX-42 in infants born at <27 weeks of GA at high risk for BPD
Sample Size	Target enrollment of 18 total subjects, with 3 cohorts of 6 subjects per cohort, randomly allocated 2:1 (active:placebo)
Summary of Subject Eligibility Criteria	
A subject must meet the following criteria to be eligible for the study:
 
 
Infant whose postnatal age is 3 to 14 days at randomization and meets the following criteria based on GA: 
 
23 weeks to 24 weeks 6 days: any birth weight, any oxygen requirement
 
25 weeks to 26 weeks 6 days: fraction of inspired oxygen (FiO2) ≥35% (sustained >2 hours) at any point during postnatal Days 1 to 14 AND birth weight ≤750 g
 
 
 
Endotracheally intubated and receiving mechanical ventilation
 
Not expected to be extubated within the next 24 hours after randomization
 
The subject has a parent/guardian who gives written informed consent.
 

Drug Dosage and Formulation	
UNEX-42 is a preparation of extracellular vesicles that are secreted from human bone marrow-derived mesenchymal stem cells suspended in phosphate-buffered saline. UNEX-42 is a clear liquid that is provided in appropriately sized vials and stored at -70±10°C prior to use.
 
UNEX-42 will be administered via IV infusion. Three dose cohorts will be evaluated:
 
 
Cohort 1: 1 administration of 20 pmol phospholipid/kg body weight
 
Cohort 2: 1 administration of 60 pmol phospholipid/kg body weight
 
Cohort 3: 1 administration of 200 pmol phospholipid/kg body weight
 

Control Group	Placebo (phosphate-buffered saline)
Route of Administration	IV infusion (via umbilical/central/peripheral IV line)

Procedures	
Subjects will be assessed during Screening and Baseline (prior to randomization) to determine eligibility for the study. After randomization, subjects will be monitored in the hospital through 40 Weeks PMA or the time of hospital discharge (whichever comes first).
 
The following efficacy and safety assessments will occur during the course of the study:
 
Efficacy Assessments: incidence and severity of BPD, duration of hospitalization, duration of mechanical ventilation, duration of supplemental oxygen therapy, duration of postnatal steroids, tracheal aspirate, and Respiratory Severity Score.
 
Safety Assessments: physical examination, vital signs, adverse events, predefined complications of prematurity, clinical laboratory parameters, and chest x-ray.
 
Enrollment between cohorts will pause for data review by a Data Monitoring Committee to evaluate the data available after each of the first 2 cohorts have been enrolled. Dose administration for Cohort 1 will occur such that there is an observational period of 3 days between dosing the first, second, and third subject to assure the opportunity for safety assessments in at least 1 subject on active treatment. This procedure will be followed for each cohort.
 
Subjects that complete the Post-treatment Phase (including those that are discharged from hospital prior to 40 Weeks PMA) will continue into the Long-term Outcome Phase and will be assessed through 1 year of corrected age.

Statistical Considerations	No formal sample size calculations were performed. Categorical assessments (eg, adverse events, death, incidence and severity of BPD) will be summarized with frequencies (number and percentage) by dose cohort and placebo. Descriptive statistics (eg, mean, standard deviation, median, interquartile range) will be calculated to summarize continuous assessments (eg, vital signs, duration of hospitalization, clinical laboratory parameters) by dose cohort and placebo. Kaplan-Meier curves will be constructed for time to event variables (eg, time to discharge from the hospital).
Sponsor	United Therapeutics Corporation [name]

**LIST OF ABBREVIATIONS**

Abbreviation	Definition
AE	Adverse event
BPD	Bronchopulmonary dysplasia
CSM	Clinical study material
CTCAE	Common Terminology Criteria for Adverse Events
CXR	Chest x-ray
DLT	Dose-limiting toxicity
DMC	Data Monitoring Committee
eCRF	Electronic Case Report Form
EDC	Electronic Data Capture
FDA	Food and Drug Administration
FiO 2	Fraction of inspired oxygen
GA	Gestational age
GCP	Good Clinical Practice
ICF	Informed Consent Form
ICH	International Council for Harmonisation
IEC	Independent Ethics Committee
IRB	Institutional Review Board
IRT	Interactive Response Technology
IV	Intravenous
MedDRA	Medical Dictionary for Regulatory Activities
MSC	Mesenchymal stem cell
NCI	National Cancer Institute
PDA	Patent ductus arteriosus
PMA	Postmenstrual age
RDS	Respiratory distress syndrome
RSS	Respiratory Severity Score
SAE	Serious adverse event
SAR	Serious adverse reaction
TEAE	Treatment-emergent adverse event

## 1 BACKGROUND AND RATIONALE

### 1.1 DEFINITION OF CLINICAL PROBLEM

Respiratory distress syndrome (RDS) is the failure to develop functional residual capacity and the propensity of affected lungs to become atelectatic. Preterm infants born prior to 28 weeks of gestational age (GA), and of very low birthweight, are at an increased risk for developing RDS (Torchin 2016). Surfactant production is low in these infants, and as such, lung recruitment and compliance are compromised. As a result, the atelectatic alveoli are well perfused but poorly ventilated, resulting in hypoxia. The clinical manifestations of RDS appear within minutes of birth and are recognized by respiratory distress associated with cyanosis often requiring respiratory support and/or resuscitation. Symptoms of RDS include low blood oxygen, low blood pH, apnea/tachypnea, atelectasis, and “ground glass” appearance of the lungs on chest x-ray (CXR). These infants are typically treated with supplemental oxygen and continuous positive airway pressure to reduce or reverse the hypoxia and acidosis. If needed, infants are intubated, given surfactant, and mechanical ventilation is employed. While these interventional strategies improve lung compliance and increase blood oxygen level, mechanical ventilation and supplemental oxygen can inadvertently cause additional lung tissue damage (Jobe 2001).

RDS in preterm infants, if unresolved, is likely to result in bronchopulmonary dysplasia (BPD). BPD is characterized by an inflammatory process causing abnormal lung development and decreased vascular and alveolar development (Collins 2017). Improvements in neonatal care has led to better survival rates of premature infants, yet the cost of this improved survival is an increased risk of developing BPD. While the definition has changed with improvements in assisted ventilation resulting in less barotrauma and oxidative injury, BPD (formerly known as chronic lung disease of prematurity) is currently defined as those infants requiring supplemental oxygen therapy for at least 28 days after birth. Furthermore, the severity of BPD for infants born at less than 32 weeks of gestation is determined by the level of supplemental oxygen required to maintain adequate blood gas oxygen levels at 36 weeks corrected GA. Infants requiring greater than 30% oxygen supplementation and/or continuous positive airway pressure are classified as severe, those requiring less than 30% oxygen are classified as moderate, and those not requiring oxygen supplementation are classified as mild (Jobe 2001).

BPD is associated with increased rates of mortality, pulmonary hypertension, emphysema, and neurodevelopmental abnormalities. Currently employed prevention strategies include the use of antenatal glucocorticoids, treatment of RDS with surfactant, and supportive treatments such as gentler, noninvasive ventilatory modalities and fluid restriction. Additional therapeutic approaches have been evaluated for preventing BPD including postnatal corticosteroids, late surfactant administration, inhaled nitric oxide, and anti-inflammatory agents such as docosahexaenoic acid. However, many of these treatments have been shown to be either relatively ineffective (Collins 2017; Ballard 2014; Donohue 2011) or controversial (Watterberg 2010). An effective therapy to prevent the development of BPD is an unmet medical need.

## 1.2 UNEX-42 BACKGROUND

UNEX-42 is a preparation of extracellular vesicles that are secreted from primary, nonimmortalized human bone marrow-derived mesenchymal stem cells (MSCs). UNEX-42 contains key molecular components (eg, ribonucleic acid, protein, phospholipids) that drive biological responses in target cells, which regulate immune modulation, angiogenesis, cellular salvage, and cellular metabolism. Activity of UNEX-42 in animal models of BPD, as well as evidence from in vitro analyses, support the continued investigation of UNEX-42 as a potential therapeutic intervention for BPD in neonates.

MSC-derived extracellular vesicles are wholly sufficient in driving improved outcomes in models of acute kidney injury (Bruno 2009; Gatti 2011), myocardial ischemia/reperfusion injury (Lai 2010), and hypoxia-induced pulmonary hypertension (Lee 2012). In a neonatal hyperoxia mouse model, MSC-derived extracellular vesicles were effective in reducing lung inflammation and alveolar simplification, thus attenuating the development of BPD (Willis 2018). These studies and others provide a strong foundation for the continued development of extracellular vesicle-based therapies. Clinically, MSC-derived exosomes have been used in 1 patient to treat therapy-refractory graft-versus-host disease. The patient was administered exosomes every 2 to 3 days over a 2-week period. All applications were tolerated well with no observed side effects (Kordelas 2014). UNEX-42 specifically has not been evaluated clinically.

### **1.3 RATIONALE FOR DEVELOPMENT OF STUDY DRUG IN DISEASE/CONDITION**

There are currently no approved prophylactic interventions for BPD, and the preventative therapies employed are largely ineffective (Beam 2014). The lack of preventative treatment options is in stark contrast to the poor outcomes observed in patients who develop severe BPD, who are at further risk for developing pulmonary hypertension, emphysema, and neurodevelopmental abnormalities. These risks in the population susceptible to developing BPD, and the lack of effective preventative treatment options, make premature infants the population with the most favorable risk-potential benefit profile.

United Therapeutics Corporation believes that safety data available from the most similar comparator under study in a similar population justifies the first-in-human study of UNEX-42 being conducted in premature infants. This comparator study used an intratracheal administration of human umbilical cord blood-derived MSCs to determine safety and inflammatory biomarkers in premature infants at risk for BPD. The study indicated that the treatment was well tolerated by all subjects with no immediate cardiorespiratory compromise or long-term adverse effects after dosing (Chang 2014, Ahn 2017). UNEX-42, which is acellular, should have an improved safety profile over the comparator cell program. United Therapeutics Corporation believes that a product consisting of extracellular vesicles presents less risk of tumorigenesis, less risk of embolus, and less risk of immunological reaction as compared to whole MSCs. As such, United Therapeutics Corporation expects a favorable safety profile.

No adverse reactions to UNEX-42 have been observed in animal studies to date. Toxicity studies conducted in neonatal rats concluded that the no-observed-adverse-effect level for UNEX-42 is 878 pmol phospholipid/kg. This level was the highest feasible dose based on the upper limit of volume that could be administered to the rats. Using the no-observed-adverse-effect level as a benchmark, the starting clinical dose for this study is 20 pmol phospholipid/kg body weight, which takes into account a human equivalent dose conversion factor of 0.22, as well as a 10-fold safety margin.

## 1.4 CLINICAL HYPOTHESIS

The hypothesis of this study is that UNEX-42 can be administered to preterm infants at high risk for BPD at doses that provide a potential for therapeutic benefit in association with an acceptable safety profile.

## 2 OBJECTIVES

### 2.1 PRIMARY OBJECTIVES

To assess the safety and tolerability of intravenous (IV) infusion of UNEX-42 in infants born at <27 weeks of GA and exhibiting respiratory distress.

### 2.2 SECONDARY OBJECTIVES

[figure not shown]
To assess the effect of UNEX-42 on the following:

1. Incidence and severity (mild, moderate, severe) of BPD or death at 36 weeks postmenstrual age (PMA)
2. Short-term outcomes including oxygen utilization and ventilation exposure in the first 28 days after treatment.
3. Long-term outcomes up to 1 year corrected age.

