c Subjects that discontinue the study prematurely should have the 40 Weeks PMA/Hospital Discharge assessments performed if possible. Subjects that complete the 40 Weeks PMA assessment or are discharged from hospital will continue into the Long-term Outcome Phase shown in [Table 3-2](#).

d The most recent CXRs prior to randomization and 36 Weeks PMA can be used.

e Clinical laboratory assessments will consist of a complete blood count, differential count, sodium, potassium, chloride, bicarbonate, blood urea nitrogen, creatinine, aspartate aminotransferase, alanine aminotransferase, and total and indirect bilirubin. For Baseline, the clinical laboratory assessments may utilize the laboratory assessments obtained as standard of care treatment within the last 24 hours in lieu of drawing blood for the sole purpose of the study. Any study-required blood tests should be obtained at the same time a blood sample is being collected for clinical purposes, if possible.

f On Day 1, vital signs are to be collected just prior to dosing, at the midpoint of dosing, just after the end of dosing, and at least once every hour for the first 4 hours after dosing is completed. Vital signs are to include heart rate, respiratory rate (either spontaneous rate or the sum of spontaneous rate and mechanically delivered rate), and systemic blood pressure (systolic and diastolic).

g Mean airway pressure is only to be collected from subjects undergoing mechanical ventilation.

h Oxygen saturation should be measured from a post-ductal location and should be consistently obtained post-ductally throughout the study period.

i The RSS should be calculated as the mean airway pressure multiplied by FiO2. Mean airway pressure and FiO2 will be collected at the same time, and the RSS will only be calculated when the subject has an obtainable mean airway pressure.

j A tracheal aspirate will be collected as possible at Baseline (prior to dosing), 72 hours postdose (if still intubated), and 7 days postdose (if still intubated).

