k All AEs will be documented from the time of informed consent until the time screen failure is documented, or until the subject is either discontinued from the study or all 40 Weeks PMA/Hospital Discharge assessments have been completed and should be followed until either resolution (or return to normal or baseline values), until they are judged by the Investigator to no longer be clinically significant, or for at least 30 days if the AE extends beyond the Post-treatment Phase.

l UNEX-42 or placebo will be administered after all other Day 1 assessments are completed, with the exception of vital signs (see footnote f).

m This assessment to be performed at 36 Weeks PMA or at Hospital Discharge, whichever comes first (see Section [3.3.1](#)).

n For each parameter, the total number of days from Baseline to the 40 Weeks PMA/Hospital Discharge will be calculated.

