**Table 3-3 Definition of Bronchopulmonary Dysplasia: Diagnostic Criteria for Gestational Age at Birth <32 Weeks**

BPD Severity	Criteria (Treatment with oxygen >21% for at least 28 days plus)
Mild BPD	Breathing room air at 36 weeks PMA or hospital discharge, whichever comes first
Moderate BPD	Need for <30% oxygen at 36 weeks PMA or hospital discharge, whichever comes first
Severe BPD	Need for ≥30% oxygen and/or positive pressure (positive-pressure ventilation or nasal continuous positive airway pressure) at 36 weeks PMA or hospital discharge, whichever comes first

Abbreviations: BPD, bronchopulmonary dysplasia; PMA, postmenstrual age

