##### 3.3.1.4 Duration of Supplemental Oxygen Therapy

The number of days of supplemental oxygen therapy use (consecutive or nonconsecutive) will be determined between Baseline and the 40 Weeks PMA/Hospital Discharge assessment.

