### 10.1 BPD ASSESSMENT

The listing for the BPD assessment at 36 weeks PMA will include the subject number, treatment group, date of assessment, whether BPD occurred, the severity of BPD (mild, moderate, severe), and predefined complications of prematurity during the Post-treatment Phase (diagnosis of sepsis, pneumothorax, clinically significant patent ductus arteriosus requiring treatment or ligation, necrotizing enterocolitis requiring treatment or surgery, intraventricular hemorrhage [including highest grade], periventricular leukomalacia, and retinopathy of prematurity [including stage]). The dates started/stopped will also be included for the predefined complications of prematurity, if available and indication of ongoing if known.

Additionally, a listing of Respiratory Severity Score will be provided. It will include the subject number, treatment group, date/time of assessment, Respiratory Severity Score, mean airway pressure, and fraction of inspired oxygen.

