## **11.6 RESPIRATORY SUPPORT**

A listing for respiratory support will include the subject number, treatment group, type of respiratory support, percent of oxygen at start and stop, and start date and stop date or ongoing at 40 weeks/hospital discharge.

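### Do the SAP listings have to give an exact count of oxygen days to serve the 28-day secondary objective?

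*Protocol*

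**What the plan says.** Protocol 2.2 sets the objective as "Short-term outcomes including oxygen utilization and ventilation exposure in the first 28 days after treatment", and SAP 2.1.2 repeats it. The protocol's oxygen measure has a different window. Section 3.3.1.4 says "The number of days of supplemental oxygen therapy use (consecutive or nonconsecutive) will be determined between Baseline and" the 40-week PMA or discharge assessment. The last footnote to Table 3-1 says that for each of ventilation, oxygen and hospitalization "the total number of days from Baseline to the 40 Weeks PMA/Hospital Discharge will be calculated". SAP 2.2.2 names no oxygen or ventilation endpoint.

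SAP 1.1 explains that the study ended early with three infants randomized in the first cohort, so the output is listings without summaries or inference. Two listings carry percent oxygen:

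- Respiratory support (SAP 11.6) gives the type of support, "percent of oxygen at start and stop, and start date and stop date or ongoing at 40 weeks/hospital discharge".
- The RSS listing (SAP 10.1) gives "date/time of assessment, Respiratory Severity Score, mean airway pressure, and fraction of inspired oxygen". Table 3-1 limits it in two ways: "the RSS will only be calculated when the subject has an obtainable mean airway pressure", and "Mean airway pressure is only to be collected from subjects undergoing mechanical ventilation".

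The vital signs listing (SAP 11.5) has oxygen saturation but no FiO2. SAP section 8 commits more broadly to listing everything captured on the eCRF.

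**The concern.** With no summary tables, the listings are the whole result, so an objective that cannot be read from them is not reported. Ventilation days can be read from support type and dates, but oxygen days are harder. An infant may stay on one support type for weeks while oxygen is weaned to room air. Neither document says that crossing 21% opens a new record. The dated FiO2 readings can lapse once mechanical ventilation ends, when weaning matters most. A reader who takes the support dates as oxygen dates could overcount.

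The same quantity feeds the BPD definition. Table 3-3 opens with "Treatment with oxygen >21% for at least 28 days plus" a severity criterion, while SAP 10.1 specifies the BPD listing as occurrence and severity without the day count. At stake would be the oxygen half of one secondary objective and a reader's ability to check a BPD yes or no. No treatment-effect conclusion is involved.

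**Working it through.** The plan gives no figure to reproduce: there is no sample size calculation and no 28-day derivation. The check asks how tightly the named fields fix the number of days above 21%.

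**Scheduled readings.** Table 3-1 puts RSS on Days 1, 2, 4, 8, 15, 22, 29 and weekly after that. For a window of Days 1 to 28, the readings fall on Days 1, 2, 4, 8, 15 and 22. For Days 2 to 29, they fall on Days 2, 4, 8, 15, 22 and 29. Either way that is 6 days with a reading and 28 − 6 = 22 without, and fewer readings if mean airway pressure stops being obtainable.

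**Bounds.** Assume one support record spanning Days 1 to 28, nominal visit days, and each reading standing for its day. With unread days free:

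- lower bound = number of days read above 21%
- upper bound = 28 − number of days read at 21%

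If there is a single wean with no return to oxygen, the count runs from the last day read above 21% to the day before the first reading at 21%.

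| Readings | Unread days free | Single wean or no excursion |
|---|---|---|
| Start >21%, stop 21%, support listing alone | 1 to 28 − 1 = 27 | 1 to 27 |
| Same, RSS >21% through Day 22 | 6 to 28 − 1 = 27 | 22 to 27 |
| Same, RSS >21% to Day 8, 21% on Days 15 and 22 | 4 to 28 − 3 = 25 | 8 to 14 |
| Start and stop both >21%, support listing alone | 2 to 28 | 28 |
| Start and stop both 21%, support listing alone | 0 to 28 − 2 = 26 | 0 |

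**The BPD threshold.** Take an illustrative infant ventilated on more than 21% on Days 1 to 8, then on nasal cannula on Days 9 to 36, listed as 35% at start and 21% at stop. In Days 1 to 28 the fields fit 8 + (1 to 20) = 9 to 28 oxygen days. To Day 35 they fit 8 + (1 to 27) = 9 to 35. Randomization is at postnatal age 3 to 14 days. If every pre-dose day was on oxygen, that adds 2 to 13 days when the day of birth is Day 1, or 3 to 14 when it is Day 0:

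- adding 2 gives 11 to 37; adding 13 gives 22 to 48
- adding 3 gives 12 to 38; adding 14 gives 23 to 49

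Every interval contains 28. This is a deliberately unfavorable case: its lower end needs 35% on Day 9 and 21% on every day after.

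**Does the SAP stop at these fields?** Table 3-1 schedules duration of supplemental oxygen, its footnote requires a total, and protocol 3.3.1.4 counts nonconsecutive days. Protocol 10.1 sends assessment results to the eCRF, and SAP section 8 lists all eCRF data. Together these suggest that an oxygen total or its inputs were to be collected and would be printed. They do not prove that dated crossings of 21% exist.

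**What would be wrong in the output?** SAP 1.1, section 10 and section 11 exclude summaries and inference, and no specified listing contains a 28-day oxygen figure. An analyst who follows the SAP as written prints dates, percentages and FiO2 values as recorded, none of which the gap makes false.

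**The case for a change.** The strongest case for a change is that it is cheap and that two things do not line up. The objective is kept in both documents without an endpoint, and SAP 1.1 does not say that this objective lost its measure. The day count behind a BPD call is not specified for listing. Its starting point is also unsettled: protocol 1.1 speaks of 28 days after birth, Table 3-3 gives no origin, and the oxygen duration endpoint starts at Baseline. A few columns, a source query for three infants or one sentence in SAP 1.1 would settle it.

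The mismatch between objective and endpoints stands, and so does the point that the named fields bound the count without generally fixing it. The rest is weaker. The day count above 21% is borrowed from the BPD definition; the objective asks about oxygen utilization, and dated percentages, FiO2 and support periods describe that. It cannot be said that the count fails for any of the three infants, because their data and the eCRF are not in the documents. BPD is a clinical diagnosis made at 36 weeks PMA or discharge, and the sponsor checks eCRF data against source (protocol 10.1, 13.3). A listing does not have to let a reader re-derive it. With three infants, no added column would let the objective of assessing an effect be met.

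**Conclusion.** No change is needed. The plan lacks detail on how the 28-day objective is measured, but supplying it would gain nothing in a terminated study of three infants reported by listings. The named fields leave a range as wide as 1 to 27 of 28 days in a poor case and 8 to 14 in a better one. If start and stop lie on the same side of 21% and there was no excursion, the count is exact. A reader of three case histories can see which applies and state the range.

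This rests on two things. First, the SAP is followed as written, so no oxygen duration, summary or comparison is reported. Second, the eCRF content is unknown: if it holds an oxygen total or crossing dates, SAP section 8 brings them into the listings and the range narrows or closes; if not, the range stays and no result depends on it. A later trial that compared arms on this objective would need a defined 28-day endpoint, but that is outside this plan.
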